6.6. Study Termination or Temporary Suspension

The Sponsor reserves the right to temporarily suspend or terminate this study, in part or whole, at any time. The reasons for temporarily suspending or terminating the study may include but are not limited to:

- The incidence or severity of AEs in this or other studies indicates a potential health hazard to subjects
- Subject enrollment is unsatisfactory
- Noncompliance that might significantly jeopardize the validity or integrity of the study
- Recommendation to suspend or terminate the study by independent body such as a health authority
- Sponsor decision to terminate the study

Where required by applicable regulations, the Investigator or head of the medical institution must inform the Institutional Review Board (IRB)/International Ethics Committee (IEC) promptly and provide the reason(s) for the suspension/termination. If the study is suspended for safety reasons and it is deemed appropriate by the Sponsor to resume the study, approval from the relevant regulatory authorities (and IECs when applicable) will be obtained prior to resuming the study.

7. SELECTION AND WITHDRAWAL OF SUBJECTS

7.1. Subject Inclusion Criteria

For inclusion in the study, subjects must fulfill all of the following criteria:

- 1. Voluntarily sign and date an informed consent form, approved by an Independent Ethics Committee/Institutional Review Board, prior to the initiation of any screening or study-specific procedures.
- 2. Adult male or female, age 18 to 80 years of age (inclusive) at the time of signing the informed consent form.
- 3. Body weight \geq 40 to \leq 140 kg for all cohorts.
- 4. Diagnosis of RA for ≥ 3 months fulfilling the 2010 American College of Rheumatology (ACR)/European Union League Against Rheumatism (EULAR) classification criteria for RA and that is categorized as ACR RA functional Class 1-3.
- 5. Treated with a biological disease-modifying anti-rheumatic drug (bDMARDs) AND/OR Janus kinase inhibitor (JAKi) therapy for RA for ≥ 3 months and had inadequate response or had to discontinue bDMARD AND/OR JAKi therapy due to intolerance or toxicity, regardless of treatment duration.
- 6. Currently receiving csDMARD therapy \geq 3 months and on a stable dose for \geq 4 weeks before the first dose of investigational product.
 - a. The following csDMARDs are allowed: oral or parenteral methotrexate ([MTX]; 7.5 to 25 mg/week), sulfasalazine (\leq 3000 mg/day), hydroxychloroquine (\leq 400 mg/day), chloroquine (\leq 250 mg/day), and leflunomide (\leq 20 mg/day).
 - b. A combination of up to 2 background csDMARDs is allowed, except the combination of MTX and leflunomide.
- 7. Meets all of the following disease activity criteria:
 - a. Six or more swollen joints (based on 66 joint counts) and \geq 6 tender joints (based on 68 joint counts) at screening and baseline visits;
 - b. Level of high-sensitivity C-reactive protein \geq 3 mg/L (\geq 0.3 mg/dL) by central laboratory;
 - c. Documented seropositivity for serum RF and/or ACPA (> ULN) at Screening or by prior laboratory evaluation.
- 8. Has completed a locally approved authorized COVID-19 vaccine regimen according to local guidance at least 3 weeks before the first dose of investigational product.
- 9. Must have discontinued all bDMARDs or JAKi prior to the first dose of investigational product. The washout period for bDMARDs or JAKi prior to the first dose of investigational product is specified below. For bDMARDs or JAKi not listed below, washout should be at least 5 times the mean elimination half-life of a drug:
 - d. \geq 4 weeks for etanercept;
 - e. \geq 8 weeks for adalimumab, infliximab, certolizumab, golimumab, abatacept, tocilizumab, and sarilumab;

- f. ≥ 1 year for rituximab;
- g. ≥ 2 weeks for JAKi (either investigational or commercially available treatment).
- 10. For potential participants already receiving opiate analgesia, the dose must be limited to no greater than 50 mg oral-morphine-equivalents per day (50 MME/day).
- 11. If female, must be either postmenopausal (defined as no menses for 12 months without other medical cause), permanently surgically sterile, or, for women of childbearing potential, must practice at least one highly effective method of contraception that is effective from study Day 1 through at least 30 days after the EOS visit (additional local requirements may apply). Sexually active female subjects must be:
 - Nonpregnant, nonlactating, and having agreed to use a highly effective method of contraception from the screening visit until 30 days after EOS visit.
 - o Note: highly effective methods of contraception include:
 - hormonal contraceptives associated with inhibition of ovulation (stable dose for at least 4 weeks prior to first dose of investigational product)
 - intrauterine device
 - intrauterine system
 - bilateral tubal occlusion
 - vasectomized male partner
 - abstinence from heterosexual intercourse
- 12. Sexually active male subjects must have documented vasectomy or must agree to use a condom or highly effective method of contraception as defined above with their partners of childbearing potential from first dose of investigational product until 30 days after EOS visit.
- 13. Male subjects must agree to refrain from donating sperm from first dose until 30 days after the last study drug administration. Female subjects must agree to refrain from donating eggs from first dose of investigational product until 30 days after EOS visit.
- 14. Female subjects of childbearing potential must have a negative serum β-human chorionic gonadotropin (β-hCG) test at the screening visit and negative urine pregnancy test on Day 1.

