4.3.1. Cohorts 1 and 2 Dose Justification

The Cohort 1 starting dose was selected based on the following factors.

[figure not shown]
- 1. Pharmacodynamics: Analysis of receptor occupancy (RO) data from study KPL-404-C101 demonstrated full CD40 RO (≥ 90%) saturation with varying durations across the evaluated dose levels. For IV doses (0.3, 1, 3, and 10 mg/kg), full CD40 RO was maintained through Days 2, 9, 29, and 71, respectively. For SC doses (1 and 5 mg/kg SC), full CD40 RO was maintained through Days 9 and 43, respectively. Analysis of the T-cell-dependent antibody response (TDAR) to keyhole limpet hemocyanin (KLH) demonstrated that single IV doses of 1, 3, and 10 mg/kg completely suppressed TDAR to primary KLH challenge through Days 9, 36, and 57 (last time point analyzed), respectively. Similarly, single SC doses of 1 and 5 mg/kg completely suppressed TDAR to primary KLH challenge through Days 9 and 29 (last time point analyzed), respectively, justifying a bi-weekly dosing frequency for all dose levels to be studied.
- 2. Safety Profile: The safety profile of the single ascending-dose study in healthy subjects (KPL-404-C101): single doses up to 10 mg/kg IV and 5 mg/kg SC were assessed. There were no deaths or related serious adverse events (SAEs), the only serious event being a patellar fracture related to a fall. There were no AEs observed that would limit dosing.
- 3. Pharmacokinetics: To evaluate optimal dosing regimens for Phase 2 clinical studies, a population PK model was developed using KPL-404 concentration-time data from healthy volunteers in Study KPL-404-C101. This population PK model simulated PK profiles for dose levels of 2.5, 5, and 10 mg/kg SC administered q2wk and for the dose level of 5 mg/kg SC administered every week (qwk) (Figure 1).

The model assumed a target mean trough concentration (C_{trough}) of 40 µg/mL as the preliminary estimate for a minimum efficacious plasma concentration (C_{eff}), consistent with the threshold established for similar assets in this class of anti-CD40 monoclonal antibody therapeutics (Ulrich 2018, Fisher 2020). Results from the simulations suggested that steady state concentrations would be achieved at/after approximately 8 weeks in all SC scenarios tested. Mean C_{trough} were predicted to be > 40 µg/mL for all SC dose levels examined when administered qwk. Mean C_{trough} were predicted to be > 40 µg/mL for KPL-404 dose levels \geq 5 mg/kg SC when administered q2wk.

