The simulated PK profiles for KPL-404 2.5 mg/kg q2wk had a mean maximum serum concentration (C_{max}) and an area under the serum concentration-time curve from time 0 to the end of first dosing interval ($AUC_{0-\tau}$) of 17.4 µg/mL and 3971.1 µg*h/mL, respectively, and increased to 44.2 µg/mL and 11748 µg*h/mL, respectively, at steady state. The mean accumulation ratio was approximately 3-fold following multiple dose administration and appeared to be consistent across all the dose range tested.

4. Safety Margin: KPL-404 was evaluated in 8-week and 26-week repeat-dose toxicity studies in Cynomolgus monkeys. The only adverse findings in the studies were an early termination on Day 143 of one female at 97 mg/kg SC after exhibiting clinical signs of poor health for several days, and another female administered 97 mg/kg SC that exhibited bilateral uveitis associated with a small blood clot in the anterior chamber of the eye. The no-observed-adverse-effect level (NOAEL) was 12-fold higher than the starting dose in this Phase 2 study, and the systemic exposure associated with the NOAEL by the SC route was approximately 10.6-fold higher. This provides an adequate safety margin between the proposed dose range for this study relative to the nonclinical safety findings.

Figure 1: Predicted Plasma Concentration of KPL-404 by Dose Level Following Weekly and Biweekly Subcutaneous Administration

Abbreviations: QW = qwk, every week; Q2W = q2wk, every 2 weeks. Note: Shaded region represents lower limit of quantitation.

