8.2.1. COVID Vaccines

Subjects are required to have completed a COVID-19 vaccine regimen to be eligible for the study. Subjects who desire to receive any additional COVID vaccines during study must discontinue treatment and wait at least 4 months after last dose of study drug to receive the vaccine in order for KPL-404 to wash out completely.

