8.2.2. Contraception

Nonpregnant, nonlactating sexually active women of childbearing potential must agree to use a highly effective method of contraception from the screening visit until 30 days after EOS visit. Highly effective methods of contraception include:

- hormonal contraceptives associated with inhibition of ovulation (stable dose for at least 4 weeks prior to first dose)
- intrauterine device
- intrauterine system
- bilateral tubal occlusion
- vasectomized male partner
- abstinence from heterosexual intercourse

Sexually active male subjects must have documented vasectomy or must agree to use a condom or highly effective method of contraception, as defined above, with their partners of childbearing potential from first dose until 30 days after the EOS visit.

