4.5. Treatment Exposure and Compliance

The study medication administration details including the administration date and time, dose, and comments will be presented in a by-subject listing.

The following parameters related to study drug administration will be summarized with descriptive statistics by treatment group for the safety population:

- Treatment duration in weeks is defined as [(minimum of (date of last study drug +13, EOS) Day 1 + 1/7] for Cohorts 1 and 2
- Treatment duration in weeks is defined as below for Cohort 3:

- 5 mg/kg SC qwk group: [(minimum of (date of last study drug +6, EOS) Day 1 + 1)/7]
- o 5 mg/kg SC q2wk group:
 - If the last dose is 5 mg/kg, then [(minimum of (date of last study drug +13, EOS) Day 1 + 1)/7]
 - If the last dose is placebo, then [(minimum of (date of last study drug +6, EOS) Day 1 + 1)/7]
- O Placebo group: [(minimum of (date of last study drug +6, EOS) Day 1 + 1)/7]
- Treatment duration in weeks is defined as [(minimum of (date of last study drug +27, EOS) Day 1 + 1)/7] for Cohort 4
- Number of dose administrations (injections) received per subject will be summarized as 1 dose, 2 doses, 3 doses, 4 doses, 5 doses and 6 doses for Cohorts 1 and 2, up to 12 doses for Cohort 3, and up to 3 doses for Cohort 4. Treatment compliance is defined as the number of injections that the subject is actually received divided by the total number of injections that the subject is planned to take from the first injection of study medications up to the actual last injection of study medications. No imputation will be made for subjects with missing or incomplete data.

All study drug exposure data will be listed including reasons for dose not administered.

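### Criterion 13 lifts the sperm-donation restriction 91 to 112 days before male contraception and the egg-donation limit end, and gives no reason

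*Protocol*

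**What the plan says.** Protocol section 7.1 contains four reproductive limits that can be compared by end date.

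- Female contraception (criterion 11): ends 30 days after the EOS visit.
- Male contraception (criterion 12): applies "with their partners of childbearing potential from first dose of investigational product until 30 days after EOS visit". Section 8.2.2 repeats the same end date: "with their partners of childbearing potential from first dose until 30 days after the EOS visit".
- Egg donation (criterion 13, second sentence): "Female subjects must agree to refrain from donating eggs from first dose of investigational product until 30 days after EOS visit".
- Sperm donation (criterion 13, first sentence): "Male subjects must agree to refrain from donating sperm from first dose until 30 days after the last study drug administration".

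Three of the four are tied to EOS. Only sperm donation is tied to the last dose. Neither document gives a reason for the different anchor, the summary of changes for Version 6.0 does not mention it, and section 8.2.2 does not cover donation.

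**The concern.** Criterion 12 restricts conception by an exposed man through one route, and criterion 13 releases him for another route while criterion 12 is still in force. If exposure is reason enough to prevent a pregnancy in his partner, the protocol should say why it is no reason to prevent one in a recipient of donated sperm.

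The 30-day limit also falls at a time when the drug may still be active. For single SC doses of 1 and 5 mg/kg in Phase 1, section 4.3.1 reports that "full CD40 RO was maintained through Days 9 and 43, respectively". The same section says of the simulated regimens: "The mean accumulation ratio was approximately 3-fold following multiple dose administration".

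At stake is the coherence of a rule that men must accept to enter the study and that sites must explain. No endpoint, sample size or error rate is involved.

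**Working it through.** The plan states no figure for this gap, so there is none to reproduce. The check is calendar arithmetic.

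**Inputs**

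- Study day = 7 × week + 1, as in the schedules of activities.
- EOS is Week 24: 7 × 24 + 1 = Day 169.
- Cohorts 1 and 2: six doses every 2 weeks, the last at Week 10 = Day 71 (schedule of activities; SAP section 4.5).
- Cohort 3: the SAP schedule marks weekly injections from baseline to Week 11, so the last is Day 78. SAP section 4.5 agrees on the count: "up to 12 doses for Cohort 3, and up to 3 doses for Cohort 4".
- Cohort 4: three doses, the last at Week 8 = Day 57 (Protocol section 6.1).

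**Formulas**

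- Sperm-donation limit ends: last dose day + 30.
- Other limits end: 169 + 30 = Day 199.
- Gap: (169 + 30) − (last dose day + 30) = 169 − last dose day.

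| | Last dose | Sperm limit ends | Other limits end | Gap |
|---|---|---|---|---|
| Cohorts 1 and 2 | Day 71 | Day 101 | Day 199 | 98 days (14 weeks) |
| Cohort 3 | Day 78 | Day 108 | Day 199 | 91 days (13 weeks) |
| Cohort 4 | Day 57 | Day 87 | Day 199 | 112 days (16 weeks) |

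**How far the gap can move**

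- Visit windows (±2 days for dosing, ±4 days for EOS) widen the overall range to 85 days (Cohort 3: 165 − 80) through 118 days (Cohort 4: 173 − 55).
- In the Cohort 3 q2wk arm, counting from the last active injection, assumed to be at Week 10, gives 169 − 71 = 98 days.
- A man who stops after the Day 1 dose but attends Week 24 has a gap of 169 − 1 = 168 days.

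**Comparison with the drug's duration**

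- Full receptor occupancy through Day 43 after a Day 1 dose of 5 mg/kg SC is 43 − 1 = 42 days, which is 12 days beyond the 30-day limit.
- As supporting context only, section 8.2.1 tells subjects who want a further COVID vaccine to stop treatment and "wait at least 4 months after last dose of study drug to receive the vaccine in order for KPL-404 to wash out completely". Four months is 120 to 123 days. Day 199 falls 199 − 71 = 128, 199 − 78 = 121 and 199 − 57 = 142 days after the last dose in Cohorts 1 and 2, Cohort 3 and Cohort 4. The EOS-based date therefore meets that interval in Cohorts 1, 2 and 4, and in Cohort 3 it meets it or falls at most 2 days short. The sperm-donation rule gives 30 days.

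**The case against.** The strongest reply is that differing dates are not an error. The rules can all be obeyed, no male reproductive finding is reported, and the documents justify none of the reproductive windows, so whether 30 days is too short for sperm donation cannot be judged from them. This stands, and it is why the point is one of consistency and not of demonstrated risk.

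A second reply is that male contraception may run longer to protect a partner from drug in semen, which would not apply to donation in the same way. The text does not support this. Criterion 12 accepts a vasectomy, or a highly effective method such as a partner's intrauterine device, in place of a condom. Neither prevents contact with semen. As written, the criterion guards against conception.

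A third reply is that the pharmacology is limited, and much of this is fair. The Day 43 figure belongs to 5 mg/kg SC; at 1 mg/kg SC occupancy lasted to Day 9, and no figure is given for the 2 mg/kg of Cohort 1. The accumulation estimate comes from simulations that did not include the Cohort 4 regimen, which aims for lower troughs. The data come from single doses in healthy subjects, nothing links CD40 occupancy to sperm, and the 4-month figure was written for vaccination. The protocol also counts about 30 days from the last dose elsewhere: 4 weeks for live vaccines in exclusion 8, and 30 days for SAE reports after early termination. These facts weaken the supporting argument but do not explain why one man's two routes to conception have different end dates.

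Finally, an EOS-based date is undefined for a subject who never has a Week 24 visit. That is true, but criteria 11 and 12 already have this weakness.

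**Conclusion.** The concern holds. For men who complete dosing on the nominal schedule, the sperm-donation limit ends 98 days (Cohorts 1 and 2), 91 days (Cohort 3) or 112 days (Cohort 4) before male contraception and the egg-donation limit, with no stated reason. Stopping treatment early while staying in the study lengthens the gap, to 168 days at most on the nominal schedule.

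The conclusion rests on the text of criteria 11 to 13 and section 8.2.2 and on the scheduled last-dose and EOS days. It does not depend on the receptor-occupancy, accumulation or washout figures. It assumes that criterion 12 is meant to prevent conception, which is how its list of accepted methods reads. A rationale could exist outside the two documents, and the consent form was not available. The importance is low: a worthwhile tidy-up of a subject-safety rule.

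**What to change.** Change the end of the first sentence of criterion 13 so that the sperm-donation limit runs to 30 days after the EOS visit, the date already used in criteria 11 and 12 and for egg donation. It would then end on Day 199 in every cohort, and the gap would be 0 days. Check that the consent form carries the same date. If the shorter period is intended, one sentence giving the reason would also settle the point.

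Two additions are optional: repeat both donation limits in section 8.2.2, and state what date applies to criteria 11 to 13 when a subject has no EOS visit.

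The cost is one phrase and a consent-form check at the next amendment, plus a sperm-donation restriction 13 to 16 weeks longer for men who complete dosing, ending when their contraception duty already ends. No data, endpoint or analysis changes.

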7.2. Subject Exclusion Criteria

The subject may not enter the study if ANY of the following apply:

- 1. Prior exposure to any other anti-CD40/CD40L agent.
- 2. Inadequate response to 5 or more classes of advanced targeted therapies (bDMARD or tsDMARD; e.g., TNF inhibitors, IL-6 receptor inhibitors, T-cell costimulatory inhibitors, anti-CD-20 antibodies, JAK inhibitors). This does not include prior discontinuation due to drug intolerance.

- 3. Injectable corticosteroids (including intra-articular) or treatment with > 10 mg/day dose oral prednisone or equivalent within 8 weeks prior to randomization. (Note: Concomitant treatment with nonsteroidal anti-inflammatory drugs, acetaminophen, oral corticosteroids [equivalent to prednisone ≤ 10 mg/day], or inhaled corticosteroids at a stable dose ≥ 4 weeks prior to baseline for stable medical conditions is allowed and should be kept at a stable dose throughout the study.)
- 4. Has received any investigational product within 30 days or 5 half-lives, if the half-life is known, of the investigational product (whichever is longer) before the first dose of investigational product.
- 5. Concurrent enrollment in another clinical study, with the exception of observational studies.
- 6. Major surgery within 8 weeks prior to screening or planned major surgery within 6 months after baseline.
- 7. Transplanted organs (except corneal transplant performed more than 3 months prior to baseline).
- 8. Receipt of live (attenuated) vaccine within the 4 weeks before baseline or expected need of live vaccination during study participation including 4 weeks after the last dose of investigational product.
- 9. History of any arthritis with onset prior to age 16 years or current diagnosis of inflammatory joint disease other than RA (including but not limited to gout, systemic lupus erythematosus, psoriatic arthritis, axial spondyloarthritis including ankylosing spondylitis and nonradiographic axial spondyloarthritis, reactive arthritis, overlap connective tissue diseases, scleroderma, polymyositis, dermatomyositis, fibromyalgia [currently with active symptoms]). Current diagnosis of secondary Sjogren's syndrome is permitted.
- 10. Clinically significant active infection, including signs/symptoms suggestive of infection, any significant recurrent or chronic infection (including positive hepatitis C virus antibody), or any episode of infection requiring hospitalization or treatment with IV antibiotics within 12 weeks before screening, or treatment with oral anti-infectives within 14 days prior to the first dose of investigational product. Subjects with any opportunistic infection within 6 months before screening will be excluded from the study.
- 11. Presence of symptoms indicative of COVID-19 infection (according to the opinion of the Principal Investigator) unless a PCR test for COVID-19 has been reported as negative within the previous 7 days or is acquired prior to randomization.
- 12. Subjects at a high risk of infection (e.g., history of hereditary or acquired immune deficiency disorder), a history of an infected joint prosthesis at any time with that prosthesis still in situ, leg ulcers, indwelling urinary catheter, or persistent or recurrent chest infections.
- 13. Subjects testing positive for human immunodeficiency virus infection. HIV test will not be required if a subject had a previously documented negative HIV result within 8 weeks screening.

- 14. Subjects with chronic active hepatitis B infection as defined below will be excluded from the study:
 - a. Hepatitis B surface antigen positive.
 - b. Hepatitis B anti-core antibody positive but anti-surface antibody negative.
- 15. Positive (or 2 indeterminate) QuantiFERON® test results unless confirmation of prior completion of appropriate treatment for latent TB and no evidence of active TB (when possible, test should be performed at least 4 weeks after receiving an mRNA COVID-19 vaccine).
- 16. History of thromboembolic event, a significant risk of future thromboembolic events (defined as a definitive diagnosis of thrombophilia OR an unstable condition associated with an increased incidence of thrombosis, such as atrial fibrillation or anti-phospholipid syndrome). All history of thrombosis should be approved by the medical monitor.
- 17. Laboratory values meeting the following criteria within the screening period (prior to randomization) of investigational product:
 - a. Serum aspartate aminotransferase $> 3 \times$ upper limit of normal (ULN);
 - b. Serum alanine aminotransferase $> 3 \times ULN$;
 - c. Total bilirubin $> 2 \times ULN$;
 - d. Estimated glomerular filtration rate by simplified 4-variable Modification of Diet in Renal Disease formula < 40 mL/min/1.73 m²;
 - e. Absolute neutrophil count $< 1,500/\mu L;$
 - f. Hemoglobin < 9 g/dL;
 - g. Total white blood cell count $< 2,500/\mu L$;
 - h. Platelet count $< 150,000/\mu L$;
 - i. Absolute lymphocyte count $< 800/\mu L$.
- 18. Known history of allergy or reaction to any component of the KPL-404 or placebo formulation and/or other products in the same class.
- 19. History of cancer within the last 5 years from screening, except for basal and squamous cell carcinoma of the skin or in situ carcinoma of the cervix treated and considered cured.
- 20. History of clinically significant (per Investigator's judgment) drug or alcohol abuse within the last 6 months.
- 21. History of any of the following cardiovascular conditions:
 - a. Moderate to severe congestive heart failure (New York Heart Association class III or IV);
 - b. Recent (within past 6 months) cerebrovascular accident, myocardial infarction, coronary stenting;
 - c. Uncontrolled hypertension as defined by a confirmed systolic blood pressure > 160 mmHg or diastolic blood pressure > 100 mmHg.
- 22. Clinically relevant or significant electrocardiogram (ECG) abnormalities, including ECG with QT interval corrected for heart rate (QTc) > 500 msec.

23. Any condition that, in the opinion of the Investigator, could interfere with evaluation of the investigational product or interpretation of subject safety or confound the results of the study.

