4.3.3. Cohort 4 Dose Justification

Cohort 4 subjects will be randomized in a 3:2 ratio to receive fixed-mg dosing of KPL-404 SC q4wk (a 600 mg SC [or matching placebo] loading dose at the Baseline Visit followed by maintenance dosing of 400 mg SC [or matching placebo] at Week 4 and Week 8). The objective is to explore the efficacy of KPL-404 at lower trough concentrations than Cohort 3, approximating the minimum level required for T-cell-dependent antibody response suppression, as seen in Phase 1. This dosing regimen (i.e., a fixed-mg dose rather than weight-based dose) represents a different approach as compared to Cohort 3, and it does not represent a dose escalation. Rather, this fixed-mg (400 mg) administered dose provides a centered administered dose level, based upon early PK data showing a relatively neutral effect of weight on the PK of KPL-404, as would be expected given that monoclonal antibodies are large macromolecules with a volume of distribution restricted to the plasma. The 400 mg administered dose is 5 mg/kg for an average 80 kg subject. The 600 mg loading dose is intended to facilitate reaching steady state trough levels more rapidly, based on PK modeling. This regimen, based on the same modeling, is expected to provide peak plasma concentrations no greater than those projected in Cohorts 2 and 3 and trough plasma concentrations lower than the 5 mg/kg q2wk dose level in Cohort 2.

[figure not shown]

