8.2. Concomitant and Rescue Medications

Medication restrictions applicable during the treatment period are described in Section 7.2 (exclusion criteria). Prior medication will be recorded up to 60 days prior to screening and prior medication for RA will be recorded up to 1 year prior to screening. Any medicinal product prescribed or over-the-counter, taken by a subject other than the study drug, is considered concomitant medication from Baseline (Day 1) to EOS.

During the treatment period up to Day 85 (EOT), the dose of background csDMARDs and corticosteroids or a new additional csDMARD may not be increased. If a subject develops RA flares requiring increased doses and/or new RA medications (as rescue medication), the subject must discontinue IMP after informing the medical monitor.

If a subject is discontinued from IP (study treatment), he or she should complete the EOT visit and remaining scheduled study visits through Week 24, per the Schedule of Activities, for all safety and efficacy assessments. The Investigator may also request that the subject return for additional visits.

After Day 85 (EOT), the dose of background csDMARDs and corticosteroids may be adjusted or a new additional csDMARD may be added to an existing one (except for combining MTX and leflunomide) if this is clinically indicated to improve disease management, in consultation with the medical monitor.

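### After Day 85 nothing bars an unplanned live vaccine, and the 4-week post-dose figure is shorter than the protocol's own occupancy and washout intervals

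*Protocol*

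**What the plan says.** **Live vaccines.** Protocol 7.2, criterion 8, excludes a candidate who had a live vaccine in the 4 weeks before baseline, or who has an "expected need of live vaccination during study participation including 4 weeks after the last dose of investigational product". Section 8.5 treats study participation as complete at Week 24/EOS, so the test of expected need runs to Day 169 for anyone who stays. Under 7.3 only withdrawal of consent counts as leaving the study, so subjects who stop dosing are still covered.

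**During treatment.** Section 8.2 carries the entry restrictions forward: "Medication restrictions applicable during the treatment period are described in Section 7.2 (exclusion criteria". Section 7.3 provides for stopping study treatment when a safety-relevant change occurs in compliance with an entry criterion.

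**After Day 85.** The follow-up paragraph of 8.2 deals with antirheumatic background therapy only: "After Day 85 (EOT), the dose of background csDMARDs and corticosteroids may be adjusted or a new additional csDMARD may be added". Vaccines are not mentioned.

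**COVID vaccines.** Section 8.2.1 has its own rule. A subject who wants a further COVID vaccine must stop treatment and "wait at least 4 months after last dose of study drug to receive the vaccine in order for KPL-404 to wash out completely".

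**Duration of drug effect.** Section 4.3.1 reports from Phase 1: "For SC doses (1 and 5 mg/kg SC), full CD40 RO was maintained through Days 9 and 43, respectively", where full occupancy means at least 90%. It also reports that "single SC doses of 1 and 5 mg/kg completely suppressed TDAR to primary KLH challenge through Days 9 and 29 (last time point analyzed". For repeat dosing it gives a simulation result: "The mean accumulation ratio was approximately 3-fold following multiple dose administration". Section 4.3.3 says that Cohort 4 is meant to explore efficacy "at lower trough concentrations than Cohort 3, approximating the minimum level required for T-cell-dependent antibody response suppression, as seen in Phase 1".

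**The concern.** Criterion 8 asks what is foreseeable at entry. A need that arises later, such as unplanned travel or an outbreak, was not foreseen and so is not caught. During treatment 8.2 and 7.3 fill that gap. In follow-up neither does: the carry-over in 8.2 is tied to the treatment period, and the 7.3 remedy is to stop a drug that has already been stopped.

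A site asked about a live vaccine at Week 14 (Day 99) therefore finds no rule. The only live-vaccine number it can find is 4 weeks after the last dose. By Day 99 that interval has already run out in Cohorts 1, 2 and 4, and it ends a week later in Cohort 3. The protocol gives no reason why 4 weeks is enough for a live vaccine when 4 months is required before a COVID vaccine, and the reason it states for the longer interval, washout of KPL-404, is a property of the drug rather than of the vaccine.

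What is at stake is a live vaccine given while CD40 is still fully occupied or, in Cohort 4, at the trough chosen to sit near the minimum for antibody-response suppression. Background csDMARDs and corticosteroids may also be adjusted in that period. Serious infection is a named event of special interest (10.6.1.3).

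**Working it through.** The plan has no figure of its own to reproduce here. The check is calendar arithmetic, with study day = 7 × week + 1.

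**Inputs**
- End of treatment: Week 12, 7 × 12 + 1 = Day 85. End of study: Week 24, 7 × 24 + 1 = Day 169. Follow-up: 169 − 85 = 84 days.
- Last scheduled dose (Appendix 1): Day 71 (Cohorts 1 and 2, Week 10), Day 78 (Cohort 3, Week 11), Day 57 (Cohort 4, Week 8).
- Full occupancy after one 5 mg/kg SC dose (4.3.1): Day 43 − Day 1 = 42 days.
- Complete suppression of T-cell-dependent antibody response (TDAR) after the same dose: Day 29 − Day 1 = 28 days. This was the last time point analyzed, so the true duration may be longer.
- 4 weeks = 28 days. The documents do not give 4 months in days; I take 112 (16 weeks) to 122 (calendar months).

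**Results by cohort**

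| | Cohort 2 | Cohort 3 qwk | Cohort 4 |
|---|---|---|---|
| Last scheduled dose | Day 71 | Day 78 | Day 57 |
| + 28 days | Day 99 | Day 106 | Day 85 |
| + 42 days (full occupancy) | Day 113 | Day 120 | Day 99 |
| + 112 to 122 days | Day 183–193 | Day 190–200 | Day 169–179 |
| Follow-up within full occupancy | 113 − 85 = 28 days | 120 − 85 = 35 days | 99 − 85 = 14 days |
| Last dose to Day 169 | 98 days | 91 days | 112 days |
| Shortfall at Day 169 against 4 months | 14–24 days | 21–31 days | 0–10 days |

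**The 4-week figure against the other two intervals**
- Against full occupancy: 42 − 28 = 14 days short.
- Against 4 months: 112 − 28 = 84 to 122 − 28 = 94 days short.
- Against TDAR: 28 − 28 = 0, so 4 weeks ends at the last time point at which suppression was measured and still complete.

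**Who is left uncovered**
- A completer with a foreseeable need is screened out for 91 to 112 days after the last scheduled dose. That exceeds 42 days in every cohort.
- A subject with an unforeseen need is not barred on any of the 84 follow-up days.
- A subject who withdraws consent early is no longer in the study, so only the 4-week figure remains.

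**Assumptions**
- Day 1 was the dosing day in Phase 1, and the single-dose duration in healthy subjects is applied after the last dose here. The simulated 3-fold accumulation suggests that this is unlikely to overstate the duration in Cohorts 2 and 3.
- In the Cohort 3 q2wk arm the last active dose falls a week earlier if active drug is given at baseline, which gives Day 113.
- Cohort 4 is taken at 80 kg, where 400 mg equals 5 mg/kg (4.3.3).
- Cohort 1 occupancy is left out because no duration is given for 2 mg/kg (8 days at 1 mg/kg, 42 days at 5 mg/kg).

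**The case against.** **The restriction does not lapse after entry.** A reader might infer that it is purely an entry test. The documents do not support that: 8.2 applies the 7.2 restrictions during treatment, and 7.3 provides for stopping the drug. This stands, and the point is confined to the time after dosing.

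**The entry screen does not end at 4 weeks.** A reader might also infer that it does. The wording places the 4 weeks inside study participation, which 8.5 runs to Week 24. This also stands. The 4-week figure then matters mainly for early withdrawals and for sites that take it as the working number. A protocol rule cannot bind someone who has left, and misreading by sites is conjecture.

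**The comparison with COVID vaccines is borrowed.** Section 8.2.1 does not say whether its concern is vaccine response or infection. Nothing in the documents ties occupancy or TDAR to live-vaccine infection, or shows that 91 to 112 days is too short. That is correct, and it limits the strength of the point. It does not explain why the two intervals differ.

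**Other safeguards may exist.** Consent pages were removed from the review copy, and the Investigator's Brochure was not available; either may carry an instruction. Medicinal products are recorded to EOS (8.2), and serious infections must be communicated within 24 hours (10.6.1.3). Recording and reporting follow the event, however, and do not prevent it.

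None of this supplies a rule for an unforeseen live vaccine between Day 85 and Day 169.

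**Conclusion.** The concern holds in a limited form. During treatment the restriction is carried forward, and the expected-need screen reaches Week 24 for those who stay. After Day 85 nothing in the reviewed text bars an unplanned live vaccine, and the single post-dose figure for live vaccines is shorter than both the observed 42-day full occupancy and the 4-month washout in 8.2.1.

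The gap covers all 84 days of follow-up, but the part that falls within full occupancy is smaller: about 28 days in Cohort 2, 35 in Cohort 3 qwk and 14 in Cohort 4, on single-dose data and at about 80 kg for Cohort 4. It would be going too far to say that the protocol's data show live vaccination at 4 weeks to be unsafe. They show that the drug is still active then; infection risk is an inference from that.

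The documents do not give the number of subjects likely to need a live vaccine in this period, and it is probably small. No endpoint, sample size or analysis changes. Severity is minor and confidence medium, chiefly because the consent form could not be checked.

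**What to change.** 1. Check first whether the consent form already states a live-vaccine interval.
2. Add one sentence to 8.2: no live vaccine from first dose through EOS or until 4 months after the last dose, whichever is later, including after study treatment has been stopped. On the dates above, the bar would run to Day 183–193 (Cohorts 1 and 2), Day 190–200 (Cohort 3) and Day 169–179 (Cohort 4), and so would cover all of follow-up.
3. Change the 4-week figure in criterion 8 to the same interval, so that the entry screen and the conduct rule agree.
4. Tell subjects the interval when they leave the study, including at early withdrawal, since the protocol cannot bind them afterwards. Add it to the consent form if it is not there.

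The cost is amendment wording with IRB/IEC approval (14.1) across about 100 sites, and possibly a matching change to the Czech protocol version that the SAP introduction mentions. A few live vaccinations would be deferred, and a few candidates with planned live vaccination might be excluded. If an amendment is being prepared for other reasons, the change can go in with it.
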